#### 5.3.4 Replacements

Subjects who prematurely discontinue may be replaced at the Sponsor's discretion.

# 5.3.5 Sponsor or Regulatory Agency Termination of the Study

Although the Sponsor (RTI Surgical, Inc.) intends to complete the study, it reserves the right to discontinue the study at any time for clinical or administrative reasons, or if required by applicable regulatory agencies.

#### VI. Study Visits

## 6.1 Baseline/Visit 1:

After signing the approved ICF, subjects who agree to participate will have Visit 1, where eligibility will be reviewed and the staff will perform the following:

- 1. Review all inclusion/exclusion criteria
- 2. Record demographic information
- 3. Medical, Surgical, and Social history
- 4. Review of systems with Physical Exam
- 5. Vital Signs (including height and weight)
- 6. Record concomitant medications (Record medications subject has been taking within 21 days prior to baseline and through the duration of the study.
- 7. Obtain Pre-operative lateral and frontal photographs with subject sitting and standing (when physically capable). For subjects who are not able to position themselves in a specific manner for the photograph due to physical limitations, the reason for this will be recorded in the subject's study record and this will not be considered a protocol deviation.
- 8. The patient will complete the following questionnaires, while the site staff will review these forms for completion:
  - a. VAS
  - b. SF 36

# 6.2 Visit 2 (Day of Surgery):

If the day of surgery is different from the baseline visit study staff will review all inclusion/exclusion criteria to ensure the participant remains eligible for enrollment. The surgery visit must be completed within 60 days of the baseline visit. If the surgery visit does not fall within 60 days of the baseline visit, the baseline procedures must be repeated.

#### 6.2.1 Data to be collected intra-operatively:

- 1. Documentation of indication for surgery (i.e. incisional hernia, re-do hernia repair, etc.)
- 2. Documentation of size and location of hernia defect
- 3. Operative start and finish times
- 4. Determine if the subject has an active infection and if so, subject is withdrawn from study and is considered a "screen failure"

- 5. Determine if subject's abdomen is unable to be closed primarily and if so, subject is withdrawn from study and is considered a "screen failure"
- Operative procedure details including all research related information (detail in OR Notes)
   \*\*\*Make sure all details are documented in the OR note (i.e. sutures used and where, number of drains inserted and where, overlap, etc. when possible)
- 7. Type and dimensions of graft used
- 8. Product and serial numbers of graft used
- 9. Fixation procedures
- 10. Concomitant procedures
- 11. Photographic documentation of graft placement prior to closure, post-closure
- 12. Complications during surgery (note any and all complications including uncontrolled bleeding, subject becoming unstable, error with mesh placement, etc.) and record these events as AE/SAE's as applicable
- 13. Medications given during surgery

# 6.3 Visit 3 (Hospital Discharge-2 days):

- 1. General physical examination and surgical site evaluation
- 2. Lateral and frontal photographs performed with subject sitting and standing (when physically capable). For subjects who are not able to position themselves in a specific manner for the photograph due to physical limitations, the reason for this will be recorded in the subject's study record and this will not be considered a protocol deviation
- 3. Adverse events evaluation (graft failure, dehiscence, enterocutaneous fistulas, seromas, wound infection, systemic infections, bleeding, etc.)
- 4. Return to OR for additional repair or graft removal (scheduled or date of return)
- 5. Review Medications (After surgery only medications that could impact healing will be recorded including but not limited to steroids, antibiotics)
- 6. Use of Wound V.A.C.® and reason for use
- 7. Date(s) of drain(s) removal, reason for drain (s) removal (i.e. drains have been in place for 7 days and/or the 24 hour fluid collection is < 30 cc /day, or any other reason removed).
- 8. Physical evaluation for hernia recurrence
  - \*\*\*Once a subject has been diagnosed with a true hernia recurrence (either by physical exam or by CT Scan), he/she will be followed only for the planned re-operation (if indicated) and details of the etiology of the recurrence will be captured in the subject's study binder (CRF), when available. The subject will only be followed to capture information about the re-operation once a recurrence is diagnosed.

\*\*\*There is no need to capture mesh related data or to conduct follow up visits between the diagnosis of recurrence and the operation for the recurrence. If a participant is not scheduled for a re-operation, his/her study participation will end at this point and this information will be documented on the CRF.

9. Clinical evidence of eventration, implant failure, implant related complications, etc. Photographs of the surgical site may be taken to document evidence of adverse events, eventration, implant failure, implant related complications, etc.

# 6.4 Visit 4 (6 weeks Post-Operative +/-One Week):

General physical examination and surgical site evaluation

- Lateral and frontal photographs performed with subject sitting and standing (when
  physically capable). For subjects who are not able to position themselves in a specific
  manner for the photograph due to physical limitations, the reason for this will be recorded
  in the subject's study record and this will not be considered a protocol deviation
- 2. Adverse events evaluation (graft failure, dehiscence, enterocutaneous fistulas, seromas, wound infection, systemic infections, bleeding, etc.)
- 3. Return to OR for additional repair or graft removal (scheduled or date of return)
- 4. Review Medications (After surgery only medications that could impact healing will be recorded including but not limited to steroids, antibiotics)
- 5. Use of Wound V.A.C.® and reason for use.
- 6. Date(s) of drain(s) removal, reason for drain (s) removal (i.e. drains have been in place for 7 days and/or the 24 hour fluid collection is < 30 cc /day, or any other reason removed).
- 7. Physical evaluation for hernia recurrence
  - \*\*\*Once a subject has been diagnosed with a true hernia recurrence (either by physical exam or by CT Scan), he/she will be followed only for the planned re-operation (if indicated) and details of the etiology of the recurrence will be captured in the subject's study binder (CRF), when available. The subject will only be followed to capture information about the re-operation once a recurrence is diagnosed.
  - \*\*\*There is no need to capture implant related data or to conduct follow up visits between the diagnosis of recurrence and the operation for the recurrence. If a participant is not scheduled for a re-operation, his/her study participation will end at this point and this information will be documented on the CRF.
- 8. Clinical evidence of eventration, implant failure, implant related complications, etc. Photographs of the surgical site may be taken to document evidence of adverse events, eventration, implant failure, implant related complications, etc.

## 6.5 Visit 5 (3 months Post-Operative +/-14 days):

- 1. General physical examination and surgical site evaluation
- 2. Lateral and frontal photographs performed with subject sitting and standing (when physically capable). For subjects who are not able to position themselves in a specific manner for the photograph due to physical limitations, the reason for this will be recorded in the subject's study record and this will not be considered a protocol deviation
- 3. Adverse events evaluation (graft failure, dehiscence, enterocutaneous fistulas, seromas, wound infection, systemic infections, bleeding, etc.)
- 4. Return to OR for additional repair or graft removal (scheduled or date of return)
- 5. Review Medications (After surgery only medications that could impact healing will be recorded including but not limited to steroids, antibiotics)
- 6. Use of Wound V.A.C.® and reason for use.
- 7. Date(s) of drain(s) removal, reason for drain (s) removal (i.e. drains have been in place for 7 days and/or the 24 hour fluid collection is < 30 cc /day, or any other reason removed).
- 8. Patient Satisfaction form (SF-36)
- 9. Physical evaluation for hernia recurrence
  - \*\*\*Once a subject has been diagnosed with a true hernia recurrence (either by physical exam or by CT Scan), he/she will be followed only for the planned re-operation (if indicated) and details of the etiology of the recurrence will be captured in the subject's study binder (CRF), when available. The subject will only be followed to capture information about the re-operation once a recurrence is diagnosed.
  - \*\*\*There is no need to capture implant related data or to conduct follow up visits between the diagnosis of recurrence and the operation for the recurrence. If a participant is not scheduled for a re-operation, his/her study participation will end at this point and this information will be documented on the CRF.
- 10. Clinical evidence of eventration, implant failure, implant related complications, etc. Photographs of the surgical site may be taken to document evidence of adverse events, eventration, implant failure, implant related complications, etc.
- 11. VAS

## 6.6 Visit 6 (6 months Post-Operative +/-28 days):

- 1. General physical examination and surgical site evaluation
- 2. Lateral and frontal photographs performed with subject sitting and standing (when physically capable). For subjects who are not able to position themselves in a specific manner for the photograph due to physical limitations, the reason for this will be recorded in the subject's study record and this will not be considered a protocol deviation
- 3. Adverse events evaluation (graft failure, dehiscence, enterocutaneous fistulas, seromas, wound infection, systemic infections, bleeding, etc.)

- 4. Return to OR for additional repair or graft removal (scheduled or date of return)
- 5. Review Medications (After surgery only medications that could impact healing will be recorded including but not limited to steroids, antibiotics)
- 6. Use of Wound V.A.C. and reason for use.
- 7. Date(s) of drain(s) removal, reason for drain (s) removal (i.e. drains have been in place for 7 days and/or the 24 hour fluid collection is < 30 cc /day, or any other reason removed).
- 8. Patient Satisfaction form (SF-36)
- 9. Physical evaluation for hernia recurrence
  - \*\*\*Once a subject has been diagnosed with a true hernia recurrence (either by physical exam or by CT Scan), he/she will be followed only for the planned re-operation (if indicated) and details of the etiology of the recurrence will be captured in the subject's study binder (CRF), when available. The subject will only be followed to capture information about the re-operation once a recurrence is diagnosed.
  - \*\*\*There is no need to capture implant related data or to conduct follow up visits between the diagnosis of recurrence and the operation for the recurrence. If a participant is not scheduled for a re-operation, his/her study participation will end at this point and this information will be documented on the CRF.
- 10. Clinical evidence of eventration, implant failure, implant related complications, etc. Photographs of the surgical site may be taken to document evidence of adverse events, eventration, implant failure, implant related complications, etc.
- 11. VAS

## 6.7 Visit 7 (12 months Post-Operative +/-28 days):

- 1. General physical examination and surgical site evaluation
- 2. Lateral and frontal photographs performed with subject sitting and standing (when physically capable). For subjects who are not able to position themselves in a specific manner for the photograph due to physical limitations, the reason for this will be recorded in the subject's study record and this will not be considered a protocol deviation
- 3. Adverse events evaluation (graft failure, dehiscence, enterocutaneous fistulas, seromas, wound infection, systemic infections, bleeding, etc.)
- 4. Return to OR for additional repair or graft removal (scheduled or date of return)
- 5. Review Medications (After surgery only medications that could impact healing will be recorded including but not limited to steroids, antibiotics)
- 6. Use of Wound V.A.C.® and reason for use.
- 7. Date(s) of drain(s) removal, reason for drain (s) removal (i.e. drains have been in place for 7 days and/or the 24 hour fluid collection is < 30 cc /day, or any other reason removed).
- 8. Patient Satisfaction form (SF-36)
- 9. Physical evaluation for hernia recurrence

\*\*\*Once a subject has been diagnosed with a true hernia recurrence (either by physical exam or by CT Scan), he/she will be followed only for the planned re-operation (if indicated) and details of the etiology of the recurrence will be captured in the subject's study binder (CRF), when available. The subject will only be followed to capture information about the re-operation once a recurrence is diagnosed.

\*\*\*There is no need to capture implant related data or to conduct follow up visits between the diagnosis of recurrence and the operation for the recurrence. If a participant is not scheduled for a re-operation, his/her study participation will end at this point and this information will be documented on the CRF.

- 10. Clinical evidence of eventration, implant failure, implant related complications, etc. Photographs of the surgical site may be taken to document evidence of adverse events, eventration, implant failure, implant related complications, etc.
- 11. VAS
- 12. Patient contentment with the cosmetic results

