## 2.3 Study Duration

Subjects will participate in this study for up to two (2) years. Participants will be followed until hospital discharge and will be seen/contacted by an Investigator and/or study team member for follow up visits at six (6) weeks, three (3) months, six (6) months and 12 months and 24 months. Once a subject has been diagnosed with a true hernia recurrence (either by physical exam or by CT Scan), he/she will be followed only for the planned re-operation (if indicated) and details of the etiology of the recurrence will be captured in the subject's study binder (CRF), when available. The subject will only be followed to capture information about the re-operation once a recurrence is diagnosed.

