## 2.4.2 Secondary Endpoints

- Recurrent hernias (functional hernias) requiring surgical intervention
- True recurrence at 24 months
- Evidence of Eventration/Hernia Recurrence (Radiographic)
- Fluid collection (Seroma, Hematoma)
- Surgical Site Infections
- Systemic Infections
- Enterocutaneous Fistula
- Dehiscence
- Implant failure requiring partial or total removal
- Patient satisfaction (using the SF-36 questionnaire) at Baseline, 3 months, 6 months, 12, and 24 months.
- Days to discharge
- Pain measured using the Visual Analog Scale for discomfort at Baseline, 3 months, 6 months, 12 months, and 24 months.
- Patient contentment with the cosmetic results at 12 months, 24 months and/or at the time of study withdrawal except for patients who have been withdrawn due to recurrence.

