## 6.8 Visit 8 Phone Call Follow Up (24 months Post-Operative +/-28 days):

- 1. Recurrence Information (ask participant if they have been evaluated and or treated for recurrence)
- 2. Adverse events evaluation (graft failure, dehiscence, enterocutaneous fistulas, seromas, wound infection, systemic infections, bleeding, etc.)
- 3. Return to OR for additional repair or graft removal (scheduled or date of return)
- 4. Review Medications (After surgery only medications that could impact healing will be recorded including but not limited to steroids, antibiotics)
- 5. Use of Wound V.A.C.® and reason for use.
- 6. Patient Satisfaction form (SF-36)\*
- 7. VAS\*
- 8. Patient contentment with the cosmetic results\*

\*The subjective questionnaires entitled Visual Analog Scale (VAS), SF-36, and Patient Contentment cannot be completed visually by the subject. Therefore, for the VAS, patients will be asked to rate their pain on a scale of 1-10. Patients will be asked questions on the SF-36 and Patient Contentment and the answers will be transcribed by designated study staff.

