#### 7.3 Serious Adverse Events

An Adverse Event is serious if:

- It results in death
- It is life threatening (the subject is at immediate risk of dying from the adverse experience)
- It requires inpatient hospitalization or prolongs existing hospitalization
- It results in persistent or significant disability/incapacity
- Important medical events that may not result in death, be life-threatening, or require
  hospitalization may be considered a serious adverse device effect when, based upon
  appropriate medical judgment, they may jeopardize the subject and may require medical
  or surgical intervention to prevent one of the outcomes listed in this definition

SAEs will be recorded in the CRF if they occurred as follows:

After a subject received treatment and throughout the subject's follow-up period. After the subject's follow-up period, and for which a causal relationship to treatment with either randomization group cannot be ruled out. Follow-up period is defined as the protocol-stipulated period or, for subjects prematurely withdrawn from a study, the duration of subject's participation.

Study staff are instructed to report all SAEs to the PI and Sponsor within 24 hours of becoming aware of the SAE. All follow-up SAE reports are to be completed and provided within 7 calendar days to the Sponsor, allowing time for more complete reports.

All Serious Adverse Events (SAEs) must be reported to:

Clinical Projects RTI Surgical, Inc. [name] (P) [contact] (F) [contact] and RTI Customer Service [contact] [contact]

In addition to documenting SAEs on the Case Report Forms, a separate SAE form must also be completed. SAEs must also be reported either by telephone, email or by FAX by the Investigator, study coordinator, or other designated study personnel, or clinical research associate within twenty-four (24) hours of becoming aware of the SAE. Follow up information must be reported as it becomes available, this may include records such as subject X-Rays, Admission and Discharge summaries, etc.

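### A patient with a true recurrence and no re-operation scheduled leaves the study at diagnosis, so later re-operations within 24 months are not systematically captured for a listed secondary endpoint

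*Combined protocol and SAP*

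**What the plan says.** Section 2.4.2 lists as its first secondary endpoint "Recurrent hernias (functional hernias) requiring surgical intervention". It gives no time window. It does not say whether surgery must be judged necessary, scheduled or performed. Implant failure leading to partial or total removal is a separate item in the same list.

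Section 2.3 sets the horizon: "Subjects will participate in this study for up to two (2) years". It then limits follow-up after a true recurrence, whether found by examination or CT: "he/she will be followed only for the planned re-operation (if indicated"), and "The subject will only be followed to capture information about the re-operation once a recurrence is diagnosed".

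Sections 6.3 to 6.7 (Visits 3 to 7) and 6.9 (unplanned visits) repeat that limit in a first starred note. A second starred note says that no visits are needed between diagnosis and the operation, and adds: "If a participant is not scheduled for a re-operation, his/her study participation will end at this point".

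The 24-month telephone call (section 6.8) includes "Recurrence Information (ask participant if they have been evaluated and or treated for recurrence") and "Return to OR for additional repair or graft removal (scheduled or date of return"). Nothing extends this call to patients whose participation has already ended.

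**The concern.** The exit rule and the endpoint pull against each other. The endpoint concerns surgery for recurrence in a two-year study, yet the rule stops observation of the patients in whom such surgery could still happen. Consider a patient diagnosed at 3 months, observed for a time, and re-operated at month 10 or month 18. That operation falls inside the 24-month horizon, but no planned contact would find it. If the implant is removed at that operation, the removal is lost as well.

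Who exits depends on whether a re-operation is scheduled. Section 5.3.2 states that the surgeon is not blinded to the implant. Section II gives a blinded evaluator the task of confirming recurrence, but no section gives that evaluator a part in scheduling. The blinding protects the diagnosis and not the decision that determines further follow-up. The intention-to-treat principle in section 3.2 cannot recover data that the protocol stops collecting.

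**Working it through.** The plan gives no figure for re-operations or for this endpoint, so there is nothing to reproduce. The check is of what is collected, followed by an illustration of size.

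**Routes by which a later re-operation could be recorded after exit**

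- Scheduled visits: none, because participation has ended.
- 24-month call: not extended to these patients.
- Serious adverse events: section 7.3 has events entered in the case report form when they occur "After the subject's follow-up period, and for which a causal relationship to treatment with either randomization group cannot be ruled out". This is passive. It depends on the site hearing of the event and on a possible causal link, and it is not tied to the endpoint.

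**Unobserved time to month 24** (24 minus the month of diagnosis)

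- 6-week visit: 24 − 1.5 = 22.5 months
- 3-month visit: 24 − 3 = 21 months
- 6-month visit: 24 − 6 = 18 months
- 12-month visit: 24 − 12 = 12 months

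**Share of re-operations missed**

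Let s be the share of diagnosed true recurrences scheduled for re-operation at diagnosis, all assumed to be operated on. Let l be the share of the remainder operated on later but within 24 months. Both are assumptions, since the documents give neither.

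Share missed = (1 − s)l / [s + (1 − s)l]

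| s | l = 0.10 | l = 0.25 | l = 0.50 |
|---|---|---|---|
| 0.7 | 0.03/0.73 = 4% | 0.075/0.775 = 10% | 0.15/0.85 = 18% |
| 0.5 | 0.05/0.55 = 9% | 0.125/0.625 = 20% | 0.25/0.75 = 33% |
| 0.3 | 0.07/0.37 = 19% | 0.175/0.475 = 37% | 0.35/0.65 = 54% |

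If nearly all recurrences are scheduled at once (s = 0.9), the loss falls to 1% to 5%.

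**In patients**

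Section 3.1 gives 120 patients, and section 2.2 cites recurrence rates of 18% to 50%. That range comes from background literature and is used here only as a bracket.

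- Recurrences: 120 × 0.18 = 21.6, up to 120 × 0.50 = 60.
- With s = 0.5, the number leaving at diagnosis is 10.8 to 30.
- With l = 0.25, the number of later re-operations not recorded is 2.7 to 7.5, or about 3 to 8.

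**Between arms**

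Assume 30% recurrence in both arms (60 × 0.30 = 18 each), with 70% scheduled at diagnosis in one arm and 50% in the other. Operations counted from scheduling alone are then 18 × 0.7 = 12.6 and 18 × 0.5 = 9.0. The gap comes entirely from the assumed difference in scheduling. Nothing in the documents says that scheduling will differ.

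**The case against.** The strongest reply is that the endpoint is undefined rather than miscounted. If requiring surgery means judged at diagnosis to need it, the information is collected before exit and much less is lost. This stands: the undercount is conditional on reading the endpoint as operations performed. It also shows that the endpoint needs a definition.

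A reader might infer that the endpoint can capture only operations already planned at diagnosis. The documents do not support that. The exit rule is triggered by a true recurrence, whereas the endpoint speaks of functional hernias, a term left undefined. A patient with eventration, or with a hernia not classed as a true recurrence, stays in follow-up, and later surgery is recorded under the return-to-OR item. A recurrence first diagnosed and treated elsewhere between months 12 and 24 can be picked up at the call. A patient whose re-operation is planned but not yet dated is arguably still followed under section 2.3. The patient who is simply observed is the one who clearly exits.

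A reader might also infer that an exiting patient is entered as not requiring surgery. No text says so; the plan says only that the end of participation is documented.

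Finally, this is one of 13 secondary items in a study that section 3.1 presents as preliminary. That bears on priority. It does not restore the missing data.

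**Conclusion.** The point holds for diagnosed true recurrences with no re-operation scheduled. Participation ends, no later contact is planned, and re-operations decided on afterwards within 24 months are not systematically captured; nor are implant removals at those operations. If the endpoint means operations performed, the direction of the error is an undercount. Its size is unknown: the 4% to 54% range rests wholly on the assumed values of s and l, and the loss is smaller still if almost all recurrences are scheduled at diagnosis.

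A stronger conclusion, that the comparison between implants is biased, is tempting because the surgeon is unblinded. The documents make that possible but do not show it, and they give no direction. The primary endpoint, true recurrence at or before 1 year, is unaffected because the event is recorded before the patient leaves. This is an inexpensive improvement to a secondary endpoint and not a threat to the trial's main result.

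**What to change.** Amend section 2.3 and both starred notes in sections 6.3 to 6.7 and 6.9 together, since changing only the exit sentence would contradict the text before it. Suggested wording: *A participant with a true recurrence and no scheduled re-operation remains in contact for re-operation status, re-operation date and implant removal only. These are obtained at the remaining scheduled contacts, by telephone if needed, including the 24-month call.* State explicitly that a re-operation planned but not yet dated does not end participation. Extend section 6.8 to these patients.

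In section 2.4.2, define the endpoint as any operation for recurrence performed from index surgery to the month-24 contact, analysed by assigned arm, in randomised patients who were not intra-operative screen failures. Those screen failures (sections 2.2, 5.2.1 and 6.2.1) have no follow-up described and cannot contribute. Say how functional hernia relates to true recurrence.

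The cost is a short amendment, a brief addition to the case report form and a few extra telephone contacts. Sections 2.1 and 5.2.1 already ask patients to accept two years of follow-up. The change affects data capture only and leaves surgical decisions alone. It removes the truncation of follow-up, but not the unblinded surgeon's influence on whether to operate, which should be stated as a limitation when the endpoint is reported.
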